6.2 Assessment windows

Attempts should be made to schedule visits (assessments) on the exact date. If this is not possible, visits (assessments) should be scheduled within the windows included below.

- Screening Visit (Day 0 to -2) / For Cocoon Cam cohort Screening Visit (Day 0 to -7)
- Enrolment Visit (Day 0)
- Phone call visit (Day 7 +2 days)
- End of study visit (Day 14 +7 days)

6.3 Assessments

6.3.1 Demographics

Demographics include date of birth, sex, race and ethnicity.

6.3.2 Birth characteristics

Birth characteristics include gestational period, gestational age and mode of delivery

6.3.3 Household Characteristics

Order of the child in the household, number of siblings, subject's and sibling's child care

6.3.4 Relevant medical history (including pre-existing conditions)

Relevant medical history is defined as any relevant medical event that occurred before enrolment in the study.

Any medical condition that the subject is born with, e.g. congenital abnormality / malformations will be recorded as pre-existing condition.

Relevant medical history and pre-existing conditions will be recorded on the Relevant Medical History and Pre-Existing Condition page in the CRF, including history of any disease and the occurrence of relevant medical events and relevant surgeries in the past.

6.3.5 Relevant concomitant medications

The use of (relevant) medication due to medical history or any adverse event related to the study product must be recorded on the Concomitant Medications page in the CRF.

The Investigator must ensure that all required information is captured on this page, including:

- Name of Medication;
- Dose and unit;
- Frequency;
- Route of administration;
- Start and stop date;
- Indication: Adverse event.

6.3.6 Feeding characteristics

The Feeding characterises will be collected through self-reported feeding questionnaire by the primary caregiver. The questionnaire will collect the food type including breastfeeding, infant or follow on formula, water, beverage and complementary food intake for the period of 1 week prior to the screening visit.

6.3.7 Primary Caregivers Characteristics

Date of birth. Mobile usage, highest level of education, occupational status

6.3.8 Questionnaires

Infant's crying pattern and caregiver experience of subject's crying and/or fussing for last 7 days before enrolment will be collected through primary caregiver reported questionnaires on the mobile app at enrolment.

The primary caregiver's feedback on the use and relevance of the data provided by the LENA recorder and their feedback on the level of engagement due to the content on the COOL mobile app will be collected through self-reported questionnaires at day 7 and 14.

A daily questionnaire on the average total minutes the subject cried/fussed and the time of the day the subject cried or fussed most based on primary caregiver's perception will be collected for 14 days from enrolment through primary caregiver reported questionnaires on the mobile app.

For the primary caregiver who consented for the use of Cocoon Cam, cry and sleep time for the infants around the clock will be collected using the COOL mobile app. The usability of the Cocoon Cam by the primary caregiver will be collected through questionnaire at day 7 and 14.

At the end of the study post clinic visit, a questionnaire to understand if the information from the LENA recorder helped to objectively articulate the primary caregiver's discussion with the PI will be collected through primary caregiver reported questionnaires on the mobile app.

At the end of the study post clinic visit, a questionnaire on feedback from the HCP on the usability and relevance of the cry and fuss data generated by the LENA recorder in their daily practice will be collected. For the primary caregiver who consented for the use of Cocoon Cam, a feedback from the HCP on the usability of the Cocoon Cam will also be collected.

6.3.9 *Data from Fitbit*

Vital parameters like heartrate and sleep pattern from Fitbit of the primary caregiver.

6.3.10 *Data from Cocoon Cam*

Sleep, Crying data captured by Cocoon cam and the usage data for the Cocoon Cam app .

6.3.11 *Study compliance*

Compliance is categorized as:

- Adherence in answering to the daily questionnaire
- Use of the LENA recorder
- Adherence to the visit window

6.3.12 *End of study evaluation*

Participants may be asked for their feedback on study participation. This is voluntarily and the encoded data will not be linked to the participants. Danone Nutricia Research will use the data to improve future studies. The encoded data will not be reported as study outcome parameter.

7 PRODUCTS

7.1 Name and description of the product

LENA is a commercially available device that parents, pediatricians, speech language pathologists, and researchers use to obtain information about a child's language environment and language development. Its language statistics were validated in a large-scale study that established norms for words, turns, and vocalisations. The device is now modified to also record crying and fussing.

The LENA recorder model# 0121 used for this study is a lightweight, pocket-size, rechargeable electronic device. This recorder can be placed securely into the specially designed infant's clothing as provided by the Sponsor. The specially designed garments are washable and reusable. After 24-hour use and removal from the clothing, the recorder can be connected to the uploader, the data is uploaded to a cloud online platform and subsequently erased from the in-home recorder. The connection with the uploader also allows the recorder to be subsequently recharged. The infant's primary caregiver will be supplied with 2 identical recorders that will be used interchangeably (one recorder is recording while the other is recharging).

The COOL mobile app is a mobile application available to the primary caregiver during their period of enrollment in this study to answer questionnaires, view the cry and fuss clock generated from the LENA recorder data and to provide them insights on infant's crying and fussing.

For the cohort consenting for Fitbit and Cocoon cam, the primary caregiver will receive Fitbit and Cocoon camera as part of study product.

7.2 Summary of known and potential risks and precautions

There is no known risk from the LENA recorder , COOL mobile app, Fitbit and Cocoon Cam. The LENA Recorder has been tested extensively against U.S., European, and Australian standards. The Recorder meets or exceeds most of the device compliance standards [Appendix 2]. Cocoon camera as well meets or exceeds most of the device compliance standards [Appendix 5].

7.3 Product handling

7.3.1 Storage and distribution

The LENA recorders, Fitbit and cocoon camera are to be stored at the Site officeat room temperature, then distributed to the primary caregiver at the screening visit. An inventory of the study product is maintained to track the distribution and supplies of the LENA recorders, uploaders, specially designed garments (e.g. T-shirts), Fitbit and Cocoon Cam.

7.4 Shipping/Distribution to/from the subjects

During screening visit, primary caregiver of the subject will receive two LENA recorders, an uploader and four specially designed garments (e.g. Vest, T-shirt, onesies), Fitbit (in case the primary caregiver consent for the use of Fitbit in the study, Cocoon Cam (in case consented for Cocoon Cam) and a courier return shipping envelope. In case, the subject is screen failure after training period, the subject will return both the LENA recorders, uploader, Cocoon Cam, Fitbit and the un-used clothing. In case the subject is enrolled, at the end of the study visit the subject will return the LENA recorder and uploader at the end of the study. The primary caregiver may retain the clothing, Cocoon Cam and the Fitbit.

7.5 Product accountability and reconciliation

The Investigator agrees not to supply the study product(s) to any person except the families participating in this trial. Study product must not be traded or discarded. Used and unused study products should be returned to the Sponsor upon completion of the study and/or study exit.

8 RANDOMISATION

Not applicable

9 ASSESSMENT OF SAFETY

Safety will be assessed and reported per the ICH-GCP guidelines.

9.1 Specification of Safety Parameters

An **Adverse Event (AE)** is defined as any untoward occurrence in a subject or clinical investigation subject using the described devices (LENA recorder and/or uploader) and which **does not necessarily** have to have a causal relationship with the study product (LENA recorder and/or uploader).

The AE may be:

- A new illness
- Worsening of a concomitant illness
- An effect of the study product/Investigational Product (IP)
- A combination of two or more of these factors

Adverse events are illnesses, signs or symptoms (including an abnormal laboratory finding) occurring or worsening during the study. Adverse events can be serious or minor. They may or may not lead to the withdrawal of the subject from the study. All adverse events must be documented and assessed for intensity, seriousness and relationship to the study product.

All AEs occurring during the study that are related (Probably or Certainly) to the study product will be recorded in the case report form (eCRF). Investigators must know and record the following information about adverse events:

- Description of event
- Duration
- Frequency
- Intensity
- Seriousness
- Action taken
- Outcome and sequelae
- Relationship to study product
- SAE (Yes/No)

Surgical procedures themselves are not AEs; they are therapeutic measures for conditions that require surgery. The condition for which the surgery is required is an AE if it occurs or is detected during the study period. Planned surgical measures permitted by the clinical study protocol and the condition(s) leading to these measures are not AEs, if the condition(s) was (were) known before the start of study treatment. In the latter case, the condition should be reported in the medical history.

9.2 Intensity

Intensity of AEs can be categorized as follows:

- Mild: Symptoms hardly perceived, only slight impairment of general well-being
- Moderate: Clearly noticeable symptom(s), but tolerable without immediate relief
- Severe: Overwhelming discomfort

9.3 Seriousness

The use of the term "adverse event" does not imply a relationship with the study product or with the study. Adverse events fall into the categories "non-serious" and "serious".

A **serious adverse event** is any untoward medical occurrence which:

- Results in death
- Is life-threatening
- Requires inpatient hospitalization or prolongation of existing hospitalization
- Results in persistent or significant disability/incapacity
- Results in a congenital anomaly or birth defect during pregnancy

Any other important medical event that may not result in death, be life threatening or require hospitalization, may be considered a serious AE when, based upon appropriate medical judgment by the principle investigator or the medical doctor in the study team, the event may jeopardize the subject and may require medical or surgical intervention to prevent one of the outcomes listed above.

Non-serious: all other adverse events not corresponding to the definition of serious adverse event are considered as non-serious.

9.4 Relation to study product

The PI or their designee will assess the possibility of a causal relationship between the study product and an adverse event based on the following criteria:

- **Unrelated:** There is an evident other explanation for the AE, e.g.:
 - The AE is obviously explained by a patient's pre-existing disease;
 - The AE is in accordance with the effect or adverse effect of the concomitant medication;
 - The AE has already occurred prior to the use of the study product.
- **Unlikely relation:** Reasonable temporal relationship with the use of the study products, but there is another plausible explanation for the occurrence of the AE.
- **Probable relation:** Reasonable temporal relationship with the use of the study product and plausible reasons point to a causal relationship with the study product.
- **Certain relation:** Reasonable temporal relationship with the use of the study product and
 - There is no other explanation for the AE, and
 - Subsidence or disappearance of the AE on withdrawal of the study product use (de-challenge), and
 - Recurrence of the symptoms on re-challenge

9.5 Methods and Timeline of Safety Reporting

The period of observation for collection of AEs begins when the family receives the study products and continues throughout the duration of the study. If the Investigator detects a serious AE in a study subject after the end of the study and considers the event possibly related to prior study product, he or she should contact the study monitor or primary designated Contract Research Organisation (CRO) personnel to determine how the AE should be documented, followed-up and reported.

9.6 Procedures for Adverse Event Reporting and Documentation

9.6.1 Monitoring and Reporting of AE/SAE

Briefing instructions on adverse events monitoring and reporting will be included during the enrolment of the infant. Reporting of adverse event will be done by the primary caregiver to the Site Study staff by telephone. An appropriate telephone number will be made available to the primary caregiver for this purpose. If the PI is not also the physician in charge, the latter will be notified accordingly and will evaluate medically and assess to determine their intensity, seriousness and relationship of the adverse events. He/she will record the medical information in the AE/SAE forms including, but not limited to the subject, date, description of event, duration, frequency, intensity, seriousness, action taken, outcome and sequel, relationship to the study product.

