3.2 Study description

At screening visit, after parent(s)/ guardian(s) of potential subjects and/or legal representatives have been informed about the study, they will be requested to sign the informed consent form (ICF) prior to start of the study. After successful signing of the informed consent, the investigator will assess the eligibility of the subjects. If the subject meets all the inclusion and none of the exclusion criteria, the primary caregiver will complete a detailed questionnaire on subject's demographics, birth, family, feeding characteristics and primary caregiver's characteristics. The primary caregiver will be provided the LENA recorder kit and in case consented for Fitbit, they will be provided with the Fitbit. The primary caregiver will need to complete a training period in order to verify a subject's primary caregiver's ability to properly connect, operate and upload data using the LENA recorders and uploader. As part of the training period, the primary caregiver will do 1-2 hours of recording using the LENA recorder and successfully upload the data into the LENA cloud server through the internet. Once the study coordinator verifies that the upload is successful, the training and feasibility assessment will be considered as complete and the subject will be considered as enrolled. The primary caregiver of the enrolled subject will be provided access to the COOL mobile app and the recording period will start.

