6 STUDY PROCEDURES AND ASSESSMENTS

6.1 Procedures per visit

Screening period:

At screening visit, after parent(s) / guardian(s) of potential subjects and/or legal representatives have been informed about

the study, they will be requested to sign the informed consent form (ICF) prior to start of the study. After successful signing of the informed consent, the investigator will assess the eligibility of the subjects. If the subject meets all the inclusion and none of the exclusion criteria, the primary caregiver will complete a detailed questionnaire on subject's demographics, family characteristics, household characteristics and feeding characteristics. The primary caregiver will also complete a questionnaire about primary caregiver's characteristics. The primary caregiver will be provided the LENA recorder kit. If the primary caregiver consents for use of Fitbit, the primary caregiver will be provided with the Fitbit. The primary caregiver will be needed to complete a training period in order to verify a subject's primary caregiver's ability to properly connect, operate and upload data using the LENA recorders and uploader. As part of the training period, the primary caregiver will do 1-2 hours of recording using the LENA recorder and successfully upload the data into the LENA cloud server through internet within 2 days of screening. The study coordinator would provide support if the primary caregiver faces any challenges and have any questions. Please note that if the primary caregiver is unable to perform all of the technical prerequisites (after troubleshooting assistance is provided), they will not be able to take part in the trial and will be dismissed as a screen failure, as well as, having to return the LENA recorders and uploader and the Fitbit(if provided). Once the study coordinator verifies that the upload is successful, the training and feasibility assessment will be considered as complete and the subject will be considered as

enrolled. The primary caregiver of the enrolled subject will be provided access to the COOL mobile app and the recording period will start.

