8 ANALYSIS OF SAFETY

No medical coding was conducted for this study. All Safety Data (Adverse Events) will be performed on the ASE data set and provided in a listing.

The number (and percentages) of subjects with at least one treatment-emergent (or intervention emergent) adverse event and the number of adverse events (by causality) will be provided overall.

All adverse events and serious adverse events will be summarised in tables and listings.

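### Adverse event observation opens at device hand-over, but the only briefing described is at enrolment and the safety analysis covers enrolled infants only

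*Protocol*

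**What the plan says.** Protocol 9.5 sets the start of safety observation: "The period of observation for collection of AEs begins when the family receives the study products and continues throughout the duration of the study". Under Protocol 7.3.1 the devices are held at the site, "then distributed to the primary caregiver at the screening visit". Section 7.4 agrees: "During screening visit, primary caregiver of the subject will receive two LENA recorders, an uploader and four specially designed garments".

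Use begins before enrolment. In the training period described in Protocol 6.1, "the primary caregiver will do 1-2 hours of recording using the LENA recorder". In the Cocoon Cam cohort, limited to 5 subjects, the camera is also used for 1 day. Only when the coordinator has verified this does Protocol 3.2 say that "the training and feasibility assessment will be considered as complete and the subject will be considered as enrolled". Caregivers who cannot meet the technical requirements are screen failures (6.1) and return the devices (7.4).

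On briefing, Protocol 9.6.1 says: "Briefing instructions on adverse events monitoring and reporting will be included during the enrolment of the infant". The same section makes the caregiver's telephone call the reporting route.

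On analysis, SAP 8 says: "All Safety Data (Adverse Events) will be performed on the ASE data set and provided in a listing". SAP 4.1 names that set as all subjects enrolled, and the SAP defines no set based on receiving a device.

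**The concern.** The observation period, the briefing and the analysis set have different starting points. Observation starts at hand-over. The briefing and membership of the safety set both start at enrolment, which the protocol treats as a separate, later step.

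Two things are at stake. Detection relies on the caregiver calling the site, so a caregiver who does not yet know what to report may not report a problem with the recorder or garment at first use. In addition, a family that leaves during training, possibly because of such a problem, is inside the observation period but outside the analysis. Its event would then have no place in the SAP's Table 12 or Listing 10, although incidence of related events is a listed safety parameter (Protocol 5.4, SAP 2.6.4).

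**Working it through.** The plan states no figure on this point, so there is none to reproduce. The check compares the sections in time order and then sizes each gap.

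**Sequence**

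| Step | Timing | Source |
|---|---|---|
| Devices received, observation opens | Screening visit: Day -2 to 0, or Day -7 to 0 with Cocoon Cam | Protocol 6.2, 7.3.1, 7.4, 9.5 |
| Training use | Before enrolment: 1 to 2 hours LENA, plus 1 day Cocoon Cam in that cohort | Protocol 6.1 |
| Enrolment | Day 0, after training is verified | Protocol 3.2, 6.2 |
| Briefing | During enrolment | Protocol 9.6.1 |
| Entry to the safety set | Enrolment | SAP 4.1, 8 |

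The first two steps come before the last three.

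**Gap 1: time before the briefing**

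The calendar window is up to 2 days, or up to 7 with Cocoon Cam. Required device use within it is much shorter. With 14 days of recording:

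- LENA, assuming round-the-clock wear (Protocol 7.1 refers to 24-hour use): 14 × 24 = 336 hours. The upper end of training gives 2/(336 + 2) = 2/338 = 0.6%; the lower end gives 1/337 = 0.3%.
- LENA, assuming 16 hours of wear a day: 14 × 16 = 224 hours, and 2/226 = 0.9%.
- Cocoon Cam: 1/(1 + 14) = 1/15 = 6.7%.

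More use inside the window is possible but not required.

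**Gap 2: infants given devices but not enrolled**

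The documents give no screen-failure rate. Take the 25 planned enrolments (Protocol 10.1, SAP 2.5) and assume k further infants who receive devices and fail training. The share of infants given devices who fall outside the safety set is k/(25 + k):

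- k = 1: 1/26 = 3.8%
- k = 3: 3/28 = 10.7%
- k = 5: 5/30 = 16.7%

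**Who is affected**

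An infant who goes on to enrol is in the all-subjects-enrolled set, and SAP 8 does not exclude that infant's training-period events. For such infants the risk is non-reporting only. Exclusion from the tables and listings applies only to infants who never enrol.

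**The case against.** The strongest reply is that little can go wrong in the gap. Required LENA use before enrolment is at most 2 hours, Protocol 7.2 states no known risk from the devices, and Protocol 9.1 sends only probably or certainly related events to the eCRF. Safety is not among the study objectives, and the analysis is descriptive. All of this stands and limits the weight of the point.

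There are also partial safeguards. The coordinator supports caregivers during training and must verify the upload (6.1). Protocol 3.4 describes reporting by telephone or email for the study generally. Reporting of related serious events under 9.6.3 and 9.6.4 is not limited to enrolled infants. These reduce the chance that something important is lost, but they do not put a non-serious related event in a screen failure into any SAP output.

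A third reply is that enrolment might be meant loosely, to include consent and screening. The protocol's own definition is against this. However, the consent pages are not in the reviewed text and Protocol 11.4 says that parents are told what participation involves, so an earlier briefing cannot be excluded. The documents support saying that caregivers may be unbriefed, not that they are.

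Finally, the camera's standing is unclear. Protocol 9.1 ties the adverse event definition to the LENA recorder and uploader, while 7.1 counts the camera as study product.

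**Conclusion.** The point holds as a mismatch between Protocol 9.5, Protocol 9.6.1 and SAP 8, and its practical weight is minor. The briefing gap covers at most 2 hours of required LENA use, and 1 day of Cocoon Cam use in up to 5 subjects. The analysis gap covers infants who fail training after receiving devices: 3.8% to 16.7% of infants given devices, if 1 to 5 such infants are assumed beside 25 enrolled.

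A reader might infer more, in three ways that the documents do not support:

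- The calendar windows could be read as unbriefed device time: 2/(2 + 14) = 12.5%, or 7/(7 + 14) = 33% with Cocoon Cam. They are scheduling limits, and required use within them is far smaller.
- All training-period events could be thought lost from the analysis. Only those of never-enrolled infants are.
- Reported incidence could be said to be biased downward. That needs a related event in a family that never enrols. For example, one event among five assumed screen failures would turn 1/30 (3.3%) into 0/25. Both inputs are invented, so this shows the direction a bias would take, not that one exists.

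**What to change.** In Protocol 9.6.1, give the adverse event briefing at device hand-over during the screening visit, so that it coincides with the start of observation in 9.5. In SAP 8, define the safety set as all infants who received a study device, including those who fail training, and list events before and after enrolment separately. SAP 8 gives no start for its emergent-event count; it should state that this is device receipt.

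The briefing needs no new contact, because the family is already at the site. The real cost is that adverse event capture has to be completed for the few families who screen-fail after receiving devices. They already have to return the equipment, and SAP 4.2 already counts screen failures in the flowchart, so the added work is small. Sample size and the primary analysis are unaffected.
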